The main challenge of hysteroscopic adhesiolysis in Asherman syndrome is the high rate of reformation of adhesions, especially in those with severe adhesions, in whom the recurrence rate may be up to 62.5% (9). We recently conducted a study and found that a Foley-catheter made intrauterine balloon dilatation seemed to be effective in preventing adhesion reformation after intrauterine adhesiolysis. However, there has

never been any formal randomized, control trial designed to identify the efficacy of the intrauterine balloon dilatation in the prevention of adhesion reformation.

Objectives

In this prospective, randomized, controlled study, we wish to determine the efficacy of intrauterine balloon dilatation in the prevention of adhesion reformation when compared with the conventional management.

Null hypothesis

The null hypothesis is that intrauterine balloon dilatation therapy will not reduce the rate of adhesion reformation compared with conventional management following a primary hysteroscopic adhesiolysis procedure.

Patients

The patients will be recruited from the Hysteroscopy Center of the Fuxing Hospital, Beijing, China. Before the surgery all patients with suspected Asherman syndrome will undergo preoperative evaluations, including a detailed history of the menstrual pattern, any previous intrauterine surgery, and reproductive history, as well as trans-vaginal ultrasonography. The severity and extent of intrauterine adhesions will be scored according to a classification system recommended by the American Fertility Society (AFS) (1988 version). The inclusion criteria include [1] women aged 18–40 years; [2] moderate to severe intrauterine adhesion (AFS score ≥ 5); [3] no previous history of hysteroscopic adhesiolysis; [4] written consent obtained; and [5] agreement to have second-look hysteroscopy. The exclusion criteria include [1] minimal adhesion (AFS score < 5) and [2] previous hysteroscopic adhesiolysis.

Study Design

After the completion of hysteroscopic adhesiolysis, recruited patients will be randomized to one of the two treatment groups by computer-generated numbers: [1] having a Foley-catheter intrauterine balloon dilatation 2 weeks and 6 weeks after hysteroscopic adhesiolysis; [2] the control group without any additional treatment. A second-look hysteroscopy will be carried out in the early proliferative phase 4 weeks the surgery and a third-look hysteroscopy was carried out 8 weeks after the surgery.

Power Calculation

On the basis of the results of the two published retrospective cohort studies comparing the balloon and hormone therapy group (control group) in the prevention of adhesion reformation, we estimated that the adhesion reformation rate in the balloon group to be 20% and in the control group to be 45%. Accepting a type 1 error of 0.05, and a

type 2 error of 0.10, the number of subjects in each arm of the randomized, controlled trial would be 79. Assuming that the dropout rate to be 20%, the total number of subject to be recruited would be 100 in each arm.

Procedure

Surgical procedure

The surgery will be carried out by one of three experienced hysteroscopic surgeons with the use of a 4.5-mm rigid hysteroscope (Olympus) with 5% normal saline infusion under 100 mm Hg pressure. The procedure will be performed under general anaesthesia in a day surgery unit. Ultrasonographic guidance will be routinely used. Once the extent and severity of uterine adhesion has been assessed, the adhesions will be divided with the use of mono-polar instrument until normal uterine anatomy is achieved.

Postoperative treatments

All subjects will be treated with oral antibiotics for 5 days. In all cases hormone therapy will also begin from the day of operation, consisting of estradiol valerate at a dose of 6 mg/d for 21 days, with the addition of dydrogesterone at a dose of 10 mg/d for the last 7 days of the estrogen therapy. After the withdrawal bleed, the hormone therapy will be repeated for another cycle. Second-look hysteroscopy will be carried out in the early proliferative phase, 4 weeks after the initial operation; a third-look hysteroscopy will be carried out 8 weeks after the initial operation. After assessment of the extent and severity of any reformed adhesion, hysteroscopic adhesiolysis will also be carried out at the time of the second-look procedure, if adhesion has recurred. The surgeon who performs the second-look and third-look hysteroscopy will be blinded to the randomization.

IUB dilatation

IUB dilatation therapy will be performed according to the methodology published in the literature (10-11). In brief, a Foley catheter (size 8-12fr) will be prepared by cutting the excess catheter tip protruding beyond the balloon prior to insertion into the uterine cavity. Once the catheter has reached the fundus, 3-5mls of saline will be slowly introduced into the balloon under ultrasound guidance, in order to directly visualise the distention of the cavity and stretching and blunt dissection of any intrauterine adhesions, if present. The whole process requires merely a few minutes.

Statistical Analysis

The rate of the recurrence of adhesion in the two groups will be compared using the χ^2 test. The reduction of AFS score in the two groups will be compared using the Mann-Whitney U test. A p value of < 0.05 will be considered statistically significant. All statistical analysis will be carried out with the use of SPSS 21.0.

Outcome measures

The primary outcome measure will include the degree of intrauterine adhesions and AFS score at follow-up. The secondary outcome measures will include the menstrual improvement, need for re-operation and future reproductive outcome.

Data processing and analysis

The researchers will ensure the confidentiality of sensitive data by minimizing the number of personnel who handle subject data. In addition, computer data will be encrypted as required to maximize security, while paper documents will be locked in filing cabinets, with only authorized personnel having access to the information.

[figure not shown]
Ethical considerations

IUB dilatation has been published as a novel technique with no untoward complications identified to date (14-16). The procedure will be performed according to the methodology available in the literature and the study has gained approval from the local ethical committee (Approval Notice Number: 2016FXHEC—KY).

Consent

All subjects will be given a detailed explanation of the study and sufficient time to consider their participation. A written consent form will be signed by the patient and retained in our confidential records.

Participant patient flow

References

1. March CM. Intrauterine adhesions. *Obstet Gynecol Clin North Am* 1995;22:491–505.
2. Asherman JG. Traumatic intra-uterine adhesions. *J Obstet Gynaecol Br Emp* 1950;57:892–6.
3. Asherman JG. Amenorrhoea traumatica atretica. *J Obstet Gynaecol Br Emp* 1948;55:23–30.

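### The recurrence rate is tested without baseline severity, although severity is scored before allocation and the protocol treats it as prognostic; prespecified adjustment would guard against chance imbalance at almost no cost

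*Combined protocol and SAP*

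**What the plan says.** For the recurrence rate, the Statistical Analysis section gives one method: "The rate of the recurrence of adhesion in the two groups will be compared using the χ^2 test". For the score it says: "The reduction of AFS score in the two groups will be compared using the Mann-Whitney U test". Neither sentence names a covariate, a stratum or an adjusted analysis.

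Four other places bear on this:

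- The background paragraph before Objectives says reformation is a problem "especially in those with severe adhesions, in whom the recurrence rate may be up to 62.5% (9" (the trailing 9 is a reference number).
- The Patients section admits "moderate to severe intrauterine adhesion (AFS score ≥ 5"), so severity varies within the trial. It also states: "The severity and extent of intrauterine adhesions will be scored according to a classification system recommended by the American Fertility Society (AFS) (1988 version").
- Study Design places allocation after surgery: "After the completion of hysteroscopic adhesiolysis, recruited patients will be randomized to one of the two treatment groups by computer-generated numbers". No stratification is described.
- Power Calculation assumes 20% recurrence with the balloon and 45% in controls, with 79 women per arm, or 100 after allowing for dropout.

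**The concern.** Severity is a true baseline variable here. It decides eligibility, Surgical procedure has it assessed before the adhesions are divided, and randomisation comes later still. The score therefore exists for every randomised woman, and the protocol itself names it as a driver of the outcome.

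Nothing stated in the design or analysis protects the recurrence comparison if one arm receives more severe cases by chance. The crude difference would then partly reflect severity, and readers would ask whether the result survives adjustment. An adjusted analysis chosen after the imbalance is seen is less credible than one fixed beforehand.

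The point is confined to the recurrence rate, which carries the null hypothesis and the sample size. The AFS comparison uses reduction in score and so already draws on baseline.

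**Working it through.** **1. The plan's own figure.** The inputs from Power Calculation are 0.20 and 0.45, type 1 error 0.05 (two-sided assumed; the text does not say) and power 0.90. The mean rate is 0.325.

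- Without continuity correction: n = [1.960·√(2·0.325·0.675) + 1.282·√(0.20·0.80 + 0.45·0.55)]² / 0.25² = 71.7, so 72 per arm.
- With continuity correction: n = (71.66/4)·[1 + √(1 + 4/(71.66·0.25))]² = 79.5. This agrees with the stated 79 to within one woman.
- Power of the uncorrected chi-square at 79 per arm: Φ[(0.25·√79 − 1.960·0.6624)/0.6384] = Φ(1.447) = 92.6%.

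The planned test therefore meets its 90% target.

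**2. How often severity will be unbalanced.** Let f be the severe share, which is not in the documents; I take 30–60%. With unstratified allocation, the between-arm difference in severe share has SD √(2f(1−f)/79), which is 7.3 points at f = 0.3 and 8.0 at f = 0.5. Ten points of 79 is 7.9 women, so the gap must be at least 8 women. Simulation puts this at 19–23% of trials (14–18% at 100 per arm).

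**3. Assumptions for the comparison of tests.** Severe-control recurrence is set at 50%, 55% or the 62.5% ceiling. The moderate-control rate is then (0.45 − f·p_sev)/(1 − f), which keeps the overall control rate at 45%. For example, with f = 0.5 and p_sev = 0.625 it is (0.45 − 0.3125)/0.5 = 27.5%. A common odds ratio is solved so that the balloon arm averages 20%. There were 200,000 simulated trials per setting, with 79 per arm and no continuity correction in either test.

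**4. Power (%), chi-square / stratified (CMH) test.**

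| Severe-control recurrence | f = 0.3 | f = 0.4 | f = 0.5 | f = 0.6 |
|---|---|---|---|---|
| 50% | 92.9 / 92.7 | 92.9 / 92.7 | 92.9 / 92.8 | 92.9 / 92.9 |
| 55% | 92.9 / 92.9 | 92.9 / 93.1 | 92.9 / 93.3 | 93.0 / 93.7 |
| 62.5% | 92.9 / 93.7 | 92.9 / 94.2 | 92.8 / 94.7 | 92.9 / 95.6 |

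**5. False positives when there is no effect.** Over all trials the chi-square rejects in 4.6–4.7% and the stratified test in 4.9–5.1%. In trials with a severity gap of 10 points or more:

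| Severe-control recurrence | Chi-square | Stratified |
|---|---|---|
| 50% | 4.6–5.1% | 4.8–5.1% |
| 55% | 5.1–6.2% | 4.8–5.1% |
| 62.5% | 5.8–8.7% | 4.8–5.1% |

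Under the planned effect at 62.5%, chi-square power in those same trials drops to about 90–92%, while the stratified test keeps about 93–95%.

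**6. Shift in the estimate.** With no effect, a 10-point gap moves the crude difference by 0.10·(p_sev − p_mod). At 62.5% this runs from 0.10·(62.5 − 37.5) = 2.5 points (f = 0.3) to 0.10·(62.5 − 18.75) = 4.4 points (f = 0.6). Under the planned effect it is 2.1–3.4 points at 62.5% and 1.2–2.0 at 55%, against a planned difference of 25.

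**7. Precision.** At 62.5% under the planned effect, the SD of the crude risk difference is 0.072 and that of the adjusted one 0.067–0.070. The 95% half-width falls from 1.96·7.2 = 14.1 points to 13.1–13.8. The variance ratio (crude to adjusted) is about 1.05–1.15 at 62.5%, 1.01–1.04 at 55% and 1.00–1.01 at 50%.

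**The case against.** An unadjusted test is legitimate under randomisation, and this one exceeds its planned power. That is correct, and it is why the point is an improvement and not an error.

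The larger figures rest on a gradient that the documents do not supply. The 62.5% is a ceiling, and its comparator may include minimal adhesions, which this trial excludes. With f = 0.6 the scenario implies 62.5% against 18.75%, an odds ratio of (0.625/0.375)/(0.1875/0.8125) = 7.2; with f = 0.5 it is 4.4. This stands: the 62.5% results are an upper bound.

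The raised conditional error also has a counterpart. At 62.5%, the chi-square rejects in only about 3.4–4.3% of the trials without a 10-point gap. At f = 0.3, for instance, 0.192·5.8 + 0.808·4.3 = 4.6% overall. This stands too, but the sponsor will have one allocation, and about one in five will show such a gap.

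Three narrower points are fair. Stratified allocation is not excluded by the text, and the patient-flow figure is not visible. The calculations cover the stratified test with a two-level split, not logistic regression on the score, whose odds ratio is conditional on severity and differs from the crude one. Finally, the plan does not say whether recurrence is read at 4 or 8 weeks, which has to be settled before any model is fixed.

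**Conclusion.** The concern holds, as an optional improvement. The planned chi-square is valid (4.6–4.7% false positives overall, about 93% power at 79 per arm). Using baseline severity changes power by between −0.2 and +2.7 points and keeps the error rate near 5% in the roughly one trial in five with a 10-point severity gap, where the chi-square could reach 8.7% at the ceiling.

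These figures assume 30–60% severe cases, severe-control recurrence of 50–62.5%, a common odds ratio and unstratified allocation; none of these is given in the documents. If severity is only weakly prognostic within AFS ≥ 5, the benefit disappears and the cost is negligible. Sample size is unaffected.

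**What to change.** Before results are seen, amend the Statistical Analysis section as follows:

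- **Main comparison of the recurrence rate:** choose one of a CMH test stratified by baseline AFS category or a logistic regression with baseline AFS score as covariate. For the CMH test, write the moderate/severe boundary into the plan, since the text gives only AFS ≥ 5. For the logistic model, state how the score enters.
- **Effect measure:** a severity-adjusted risk difference, for example Mantel-Haenszel weighted, with its 95% confidence interval. This avoids resting the result on a conditional odds ratio.
- **Supporting analysis:** the unadjusted chi-square, as now planned.
- **Allocation:** if it has not begun, the computer list can be stratified by the same category. This mainly prevents imbalance and adds at most about 0.3 points of power beyond the stratified test.

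The cost is one or two sentences and a fixed boundary, with no extra data or patients. The downside is one more analysis to report and, if severity matters little, a loss of up to 0.2 points of power.

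### The named primary outcome is the follow-up AFS score, but the only AFS test is on the unadjusted reduction; test the follow-up score adjusted for the pre-operative score

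*Combined protocol and SAP*

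**What the plan says.** Outcome measures states: "The primary outcome measure will include the degree of intrauterine adhesions and AFS score at follow-up". Statistical Analysis gives two tests. One is a chi-square test on the recurrence rate. The other is the only AFS test: "The reduction of AFS score in the two groups will be compared using the Mann-Whitney U test". No test of the follow-up score and no adjustment for any covariate appears, and the starting point of the reduction is not defined.

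Four other places bear on this:

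- Study Design, on timing: "After the completion of hysteroscopic adhesiolysis, recruited patients will be randomized to one of the two treatment groups by computer-generated numbers".
- Surgical procedure, on the state of the cavity by then: "the adhesions will be divided with the use of mono-polar instrument until normal uterine anatomy is achieved".
- Null hypothesis, on the question asked: "intrauterine balloon dilatation therapy will not reduce the rate of adhesion reformation compared with conventional management".
- The background paragraph before Objectives, on reformation: "especially in those with severe adhesions, in whom the recurrence rate may be up to 62.5" per cent.

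**The concern.** The outcome and its test do not match. On the natural reading, the reduction is the pre-operative score minus the follow-up score. The pre-operative score is settled before randomisation, and the surgery has already removed the adhesions it measured. The balloon acts only on the second term, by preventing reformation or by "stretching and blunt dissection of any intrauterine adhesions, if present" (IUB dilatation section).

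Subtracting from a pre-operative score that varies between women (entry requires AFS 5 or more) adds variation unrelated to treatment. It can also place a woman whose adhesions recurred above one who stayed clear. The plan itself treats severity as prognostic, so severity belongs in the analysis as a covariate and not inside the outcome.

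At stake are the power of the AFS comparison and its readability beside the chi-square test. A significant recurrence result could sit next to a non-significant AFS result largely because of the metric.

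**Working it through.** **1. The plan's own figure.** Power Calculation gives 45% v 20% reformation, type I error 0.05, type II error 0.10, and 79 per arm. The two-sided pooled formula gives

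n = [1.960·√(2·0.325·0.675) + 1.282·√(0.45·0.55 + 0.20·0.80)]² / 0.25² = 71.7.

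With continuity correction, n = (71.7/4)·[1 + √(1 + 4/(71.7·0.25))]² = 79.5, which agrees with 79. For dropout, 79/0.8 = 98.75 and 80/0.8 = 100, so 100 per arm is consistent. This sizing rests on the recurrence rate and is not affected by how AFS is analysed.

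**2. Mis-ordering by hand.** Assume a clear cavity scores 0. Woman A goes from 5 to 0: reduction 5 − 0 = 5, no recurrence. Woman B goes from 10 to 4: reduction 10 − 4 = 6, recurrence. The test ranks B above A.

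**3. Variance.** Set the follow-up variance to 1. Let q be the ratio of pre-operative to follow-up SD, and ρ their correlation.

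- Var(reduction) = 1 + q² − 2ρq
- Var(adjusted follow-up) = 1 − ρ²
- Difference = (q − ρ)², which is zero only when q = ρ

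The documents give neither q nor ρ. Set the effect so that the adjusted analysis has 90% power at 79 per arm. The reduction then has power Φ(3.242·√(Var adjusted / Var reduction) − 1.960):

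| q | ρ = 0 | ρ = 0.3 | ρ = 0.5 | ρ = 0.7 |
|---|---|---|---|---|
| 0.5 | 83% | 89% | 90% | 88% |
| 1.0 | 63% | 74% | 80% | 85% |
| 1.5 | 44% | 52% | 56% | 58% |

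This is a result for means; rank tests on skewed scores need simulation.

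**4. Simulation set-up.** From the plan: 79 per arm, recurrence 45% v 20%, AFS at least 5. Assumed: pre-operative AFS uniform from 5 to 6, 8, 10 or 12; the reformed score mild (1-4), uniform below baseline, or within 2 points of baseline; clear cavities scored 0 or 0-2. Tests: tie-corrected Mann-Whitney on the reduction, the same on the follow-up score, and rank analysis of covariance (mid-ranks of both scores, follow-up ranks regressed on pre-operative ranks, residuals compared by two-sample t). The ranges below span chosen scenarios; they are not probabilities.

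**5. Slope tied to the background paragraph.** The more severe half of controls recurs at 62.5%, with 45% overall. The log-odds slopes needed are 1.480, 0.766, 0.514 and 0.386 per point for the four baseline ranges. Power, 5,000 trials per scenario:

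| Clear score | Reformation | Reduction | Rank ANCOVA |
|---|---|---|---|
| 0 | mild | 35-89% | 94-95% |
| 0 | uniform | 71-90% | 93-95% |
| 0 | near baseline | 92% | 94-95% |
| 0-2 | mild | 15-46% | 47-49% |
| 0-2 | uniform | 52-56% | 51-66% |
| 0-2 | near baseline | 86-92% | 81-83% |

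**6. Log-odds slope 0, 0.3 or 0.6 per point** (72 scenarios, 5,000 trials each, Monte Carlo SE at most 0.7 points):

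| Clear score | Quantity | Reduction | Follow-up, unadjusted | Rank ANCOVA |
|---|---|---|---|---|
| 0 | power | 27-95% | 88-92% | 91-97% |
| 0-2 | power | 14-95% | 46-81% | 46-86% |
| 0 | chi-square significant, AFS test not | 2.1-65.5% | 1.6-5.2% | 0.8-2.5% |
| 0-2 | chi-square significant, AFS test not | 2.5-80.1% | 13.4-48.1% | 10.9-48.1% |

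With clear cavities at 0, rank ANCOVA is 1-64 points above the reduction in every scenario. The worst case for the fix is baseline 5-12, reformation near baseline, slope 0.6 and clear 0-2: reduction 94.6%, unadjusted follow-up 75.4%, rank ANCOVA 85.5%.

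With clear cavities at 0, the reduction ranks a recurrer strictly above a clear woman in 0-44% of such pairs (mild), 0-20% (uniform) and 0% (near baseline). With rank ANCOVA residuals the figure is under 1%.

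**7. Balloon also lowering reformed scores by 2 points** (3,000 trials per scenario). Reduction v rank ANCOVA: clear 0, 48.2-99.6% v 96.9-99.8%; clear 0-2, 29.1-99.5% v 85.0-98.2%. The reduction is up to 6 points ahead, near baseline only.

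**8. Null** (32.5% in both arms, 10,000 trials per scenario). Rejection is 4.6-5.3% for the reduction, 4.7-5.4% for the unadjusted follow-up score, 4.6-5.4% for rank ANCOVA and 4.7-5.6% for chi-square.

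**The case against.** The strongest reply is that little hangs on this. The null hypothesis and sample size concern the reformation rate, which the chi-square test addresses directly, and randomisation makes the expected difference in mean reduction equal to that in mean follow-up score. Both points are true and limit the weight. But the Mann-Whitney test ranks individual women rather than comparing means, and those ranks can put a recurrence above a clear cavity.

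The power figures rest on assumed distributions. The 62.5% is an upper figure for an undefined severe group, so applying it to the more severe half of controls is itself an assumption. The size of the loss is therefore undetermined, and in one corner the reduction wins. With clear cavities at 0-2 and mild reformation, the adjusted test has under 50% power in the section 5 scenarios, so the metric is not the only weakness. All of this stands.

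Most of the gain comes from no longer subtracting the baseline: rank ANCOVA minus the unadjusted follow-up test is only −0.5 to +10.1 points. That is fair, but adjustment costs almost nothing and uses a score already collected. The choice between the 4-week and 8-week look is a separate gap; it enters here only because a follow-up score cannot be tested without naming the visit.

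**Conclusion.** The concern holds. The mismatch between the named outcome and its test is plain from the text and needs no assumption beyond reading the reduction as starting from the pre-operative score, the only sensible reading once anatomy has been restored. The consequence is lost power and a score that can mis-order women; validity is not affected. The loss runs from negligible to 64 points if clear cavities score 0. If they keep 0-2 points, the comparison can go either way, with the reduction up to about 9 points ahead when reformation is near the original severity and recurrence rises with severity. It should be fixed, with modest weight, because the test that sized the trial is unaffected.

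**What to change.** Replace the AFS sentence in Statistical Analysis with:

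> AFS score at the [second-look (4-week) or third-look (8-week): sponsor to name one] hysteroscopy, as recorded before any repeat adhesiolysis at that visit, will be compared between the groups adjusting for the pre-operative AFS score (rank analysis of covariance); the reduction from the pre-operative score will be summarised descriptively.

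The method should be spelled out: mid-ranks of both scores over all women, follow-up ranks regressed on pre-operative ranks, residuals compared between groups. The visit should be fixed before analysis, because Postoperative treatments says that "hysteroscopic adhesiolysis will also be carried out at the time of the second-look procedure, if adhesion has recurred", so the 8-week score also reflects that procedure.

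The cost is one sentence, two rankings and one regression, with no new data and no change to the sample size. The downside is the possible loss of about 9 points of power in the corner described above.

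### The outcomes listed as primary (adhesion degree and AFS score at an unnamed follow-up look) are not the reformation rate on which the null hypothesis and sample size rest

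*Combined protocol and SAP*

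**What the plan says.** The combined protocol and SAP describes its main question in several places.

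- **Objectives:** "we wish to determine the efficacy of intrauterine balloon dilatation in the prevention of adhesion reformation when compared with the conventional management". So the aim is about whether adhesions come back.
- **Null hypothesis:** this section frames the same aim as a rate: "The null hypothesis is that intrauterine balloon dilatation therapy will not reduce the rate of adhesion reformation compared with conventional management".
- **Power Calculation:** "we estimated that the adhesion reformation rate in the balloon group to be 20% and in the control group to be 45" (per cent). With type 1 error 0.05 and type 2 error 0.10 this gives 79 per arm, or 100 per arm after 20% dropout. Neither rate is tied to a time point.
- **Outcome measures:** "The primary outcome measure will include the degree of intrauterine adhesions and AFS score at follow-up". This is the only sentence that names a primary outcome. The reformation rate is listed as neither primary nor secondary.
- **Statistical Analysis:** a chi-square test compares recurrence rates and a Mann-Whitney U test compares the reduction in AFS score. Both are judged at p < 0.05. Neither is called primary, and no look, order or joint rule is given.

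The timing matters. The balloon arm is described as "having a Foley-catheter intrauterine balloon dilatation 2 weeks and 6 weeks after hysteroscopic adhesiolysis". The second look is at 4 weeks, and at that look "hysteroscopic adhesiolysis will also be carried out at the time of the second-look procedure, if adhesion has recurred". Then "a third-look hysteroscopy will be carried out 8 weeks after the initial operation".

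**The concern.** A primary outcome statement should let a reader identify, before any data are seen, the one result that decides the trial. Here three things are open.

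1. **Which measure.** The sizing is for a binary rate; the listed primaries are a grade and a score.
2. **Which form of the score.** The outcome section names the AFS score at follow-up, while the analysis tests its reduction. The starting point of that reduction is not stated.
3. **Which look.** Week-4 status, week-8 status and any reformation by week 8 answer different questions.

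Two things are at stake. The stated 90% power may not belong to the result that is reported as primary. And if rate and AFS score, or the two looks, disagree, the choice of headline could be made with the data in hand.

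**Working it through.** **Step 1. Reproduce the plan's 79 per arm.** Inputs from the Power Calculation: p1 = 0.45, p2 = 0.20, difference d = 0.25, mean rate 0.325, alpha 0.05 (taken as two-sided; the plan does not say), power 0.90.

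n = [1.960 × √(2 × 0.325 × 0.675) + 1.282 × √(0.45 × 0.55 + 0.20 × 0.80)]² / 0.25²
= (1.298 + 0.818)² / 0.0625 = 71.7

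With continuity correction: n' = (n/4) × [1 + √(1 + 4/(n × d))]² = (71.66/4) × (1 + √1.2233)² = 79.5.

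This matches the stated 79 to within rounding. Dropout: 79/0.80 = 98.75, against 100 stated. The sample size is therefore a comparison of two reformation proportions. No AFS quantity enters it.

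**Step 2. Power of the rate test at 79 per arm** (uncorrected chi-square, normal approximation):

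(√79 × 0.25 − 1.298) / √0.4075 = (2.222 − 1.298) / 0.638 = 1.447, so power = 92.6%.

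This holds only if 20% and 45% describe the look that is analysed. As an illustration (assumed rates), 25% v 45% gives (√79 × 0.20 − 1.322) / 0.660 = 0.691, so power = 75.5%.

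**Step 3. Compare the looks.**

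| | 4-week look | 8-week look |
|---|---|---|
| Dilatations already given (balloon arm) | week 2 only | weeks 2 and 6 |
| Adhesions divided since the primary operation | none planned | yes, if recurrence was found at the second look |

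Week-8 status is thus measured after re-treatment of the women who had recurred. Rates at the two looks need not be equal, and the documents give no rate by look.

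**Step 4. Power for AFS reduction.** The documents give no standard deviation, distribution or target difference, only entry at a score of 5 or more, so this power cannot be computed. Simulation can show only how far it depends on assumptions. Take 79 per arm, reformation in 20% v 45%, baseline AFS uniform on 5 to 12, score 0 without reformation, and six assumed patterns of reformed score.

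- Same reformed scores in both arms: AFS power about 28% to 80%.
- Balloon-arm reformed scores halved: AFS power about 47% to 97%; power to win on both tests about 45% to 91%.

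All of these scores are assumptions. The range shows that AFS power could be well below 90%, and also that it could exceed it.

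**Step 5. Error rate if a win on either test were claimed at one look.** For two two-sided 0.05 tests whose statistics are bivariate normal with correlation ρ, the chance is 1 − P(|Z1| < 1.96 and |Z2| < 1.96).

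| ρ | Either test significant, any direction | Either test significant, favouring the balloon |
|---|---|---|
| 0 | 1 − 0.95² = 9.75% | 1 − 0.975² = 4.9% |
| 0.35 | 9.4% | 4.7% |
| 0.9 | 7.0% | 3.5% |
| One test only | 5% | 2.5% |

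The correlation is not in the documents. Simulation under the null with a range of assumed AFS patterns gave about 0.35 to 0.91, so the row for ρ = 0 is an upper bound.

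**The case against.** The best defence is that the intent is plain. The objective, the null hypothesis, the sample size and the first-listed test all concern reformation, and degree of adhesions can loosely cover whether they recurred. On that reading the outcome sentence is loose wording plus one extra measure. This largely stands. The recurrence rate does have a planned test, and the sample-size arithmetic is sound. But intent settles neither which look counts nor what follows if the rate and the AFS score disagree.

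Three stronger readings are tempting, and the documents do not support them.

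- *A reader might infer that the type 1 error is already inflated to nearly 10%.* The plan states no either-wins rule, and one pre-specified rate test keeps its 5%. The 9.75% also needs independent tests, which is implausible for two measures of the same adhesions.
- *A reader might infer that the trial is underpowered for AFS reduction.* That needs an assumption about reformed scores. The IUB dilatation section describes stretching and blunt dissection of adhesions, so milder reformed disease in the balloon arm is plausible, and AFS power could then exceed 90%.
- *A reader might infer that the plan nowhere names a look.* The participant-flow figure is not shown and might name one. The point on timing applies to the readable text only. The mismatch between listed and powered outcomes would remain either way.

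It is also fair to say that a sole primary is not the only valid repair. Two primaries with a stated joint rule would serve, at a price given under the fix.

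**Conclusion.** The point holds and should be corrected before analysis. The outcomes listed as primary are not the quantity that was hypothesised and powered, and the readable text fixes no look, so the primary result is not uniquely determined.

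The stated 90% power attaches to the reformation rate alone, conditional on the planned rates applying at the chosen look or definition. For AFS reduction it is unknown, and it could be lower, for example if reformed adhesions score the same in both arms.

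The error-rate consequence is conditional. Only if a win on either measure at one look were claimed would the two-sided false-positive chance rise from 5% to about 7% to 9.4%. In the direction of balloon benefit it would rise from 2.5% to about 3.5% to 4.7%. These figures rest on normal theory and assumed correlations of 0.9 to 0.35.

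**What to change.** Change the wording of the outcome and analysis sections as follows.

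1. Name the adhesion reformation rate as the sole primary outcome, tested once by the planned chi-square test at two-sided 0.05.
2. Give it one definition: status at one named look, or any reformation by the third look.
3. State that 20% and 45% refer to that definition, or restate the power.
4. Define AFS reduction as the pre-operative score minus the score at one named look, scored before any repeat adhesiolysis. Make it, and results at any other look, secondary and unable by themselves to make the trial positive.

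**Cost.** The sample size stays at 79 (100 recruited) per arm if the planned rates apply to the chosen definition. A win on AFS alone, or at another look, is no longer a primary result. Each definition has a drawback:

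- A week-4 primary excludes any effect of the week-6 dilatation.
- A week-8 primary follows re-treatment of women who recurred.
- A cumulative primary cannot register a week-6 effect in women who recurred by week 4 (0.20 × 79, about 16 balloon women, if the planned rate is reached by then). It also needs a rule for a missed third look, because the inclusion criteria ask agreement only to the second.

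If the sponsor prefers two primaries with either allowed to win, a Bonferroni split (0.025 each) leaves 87.6% power for the rate at 79 per arm. Restoring 90% takes 85 per arm, or 93 with continuity correction, before dropout. AFS would still need its own power statement.
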